### 5.1. Year 1 Data Complete

Year 1 data are considered complete after the last patient enrolled has completed through Week 52 and the database through Week 52 has been locked. All available data will be analyzed when Year 1 data are complete. An assessment of the Year 1 data by the DMC will occur prior to releasing the randomization to the Reata analysis team. The DMC will assess the final Year 1 primary and key secondary efficacy endpoints for statistical significance prior to Reata being unblinded. This process is designed to prevent Reata from becoming unblinded to Year 1 data in the event that the Year 1 primary and key secondary endpoints do not demonstrate statistically significant evidence of efficacy. The DMC will inform Reata whether or not both the primary and key secondary efficacy endpoints demonstrate statistically significant evidence of efficacy (i.e.,  $p < 0.025$ ). If both the Year 1 primary and key secondary endpoints are not statistically significant, then Reata will not to unblind until the Year 2 data are complete. However, if both the Year 1 primary and key secondary endpoints are statistically significant, then Reata will unblind and the final analysis of Year 1 data and a preliminary assessment of Year 2 safety data will be performed as described in Section 5.1.1 and Section 5.1.2.

#### 5.1.1. Final Analysis – Year 1

At the time of Year 1 data complete, results from analyses of data through Week 52, including the primary and key secondary efficacy endpoints, are considered final. Because patients will be continuing in the trial, the interim CSR will not include by-patient data listings or patient

narratives to minimize the number of individuals having access to patients' treatment assignments.

### **5.1.2. Preliminary Analysis – Year 2**

At the time of the Year 1 data complete and prior to Year 2 data complete, many patients will have completed visits beyond Week 52. Available safety data for Year 2 visits will be summarized descriptively, including summaries of AEs, vital sign assessments, and laboratory results (including descriptive summaries of eGFR for safety). Year 2 efficacy endpoints will not be assessed with the preliminary Year 2 analysis. The interim CSR will include the preliminary Year 2 safety results.

### **5.2. Year 2 Data Complete**

Year 2 data are considered complete after the last patient enrolled has completed through Week 104 and the database through Week 104 has been locked. Year 2 efficacy endpoints will be assessed only when Year 2 data are complete. The interim CSR will be amended to add Year 2 efficacy results, and to finalize Year 2 safety results. Because the trial is complete when Year 2 data are complete, the final CSR will include by-patient data listings and patient narratives.

## **6. GENERAL CONSIDERATIONS FOR DATA ANALYSES AND HANDLING**

The efficacy and safety analyses use the analysis sets defined in Section 6.3. Patient listings (as appropriate) of all analysis data that support summary tables and/or figures are provided along with their source data. The summary tables do not include measurements from patients excluded from the pre-defined analysis sets or extra measurements (such as unscheduled or repeat assessments) not closest to the target study day unless specified otherwise, but the patient listings do include these data. Missing data are not imputed, unless otherwise specified. In general, patient listings are sorted by patient number and assessment date (time and parameter, as applicable). Any laboratory value (including eGFR), vital sign assessment, or ECG value collected after starting dialysis or after receiving a kidney transplant is considered invalid and will be treated as missing.

### **6.1. General Summary Table and Individual Subject Data Listing Considerations**

Results of statistical analyses are reported using summary tables, listings, and figures (TLFs). All TLFs will use ICH numbering conventions. The strategy for controlling the overall Type I error rate for the Year 1 and Year 2 primary and key secondary efficacy endpoints and other select exploratory endpoints is described in Section 8.4. For endpoints not described in Section 8.4, the reported significance levels are nominal and the following statistical conventions are used:

- Unless otherwise noted, all statistical testing is two-sided and is performed at the 0.05 significance level.
- Tests are declared statistically significant if the calculated p-value is  $<0.05$ .

All analyses and summaries are produced using SAS® version 9.3 (or higher).

### **6.2. Data Presentation Conventions**

Unless otherwise specified, descriptive statistics for continuous variables include the number of patients with data (N), mean, standard deviation (SD), median, minimum, and maximum. The same number of decimal places as in the observed value are presented when reporting minimum and maximum; 1 more decimal place than in the observed value is presented when reporting mean and quartiles; and 2 more decimal places than in the observed value is presented when reporting SD.

Categorical data are presented using frequency counts and percentages. All percentages are rounded to 1 decimal place, unless otherwise specified. Percentages equal to 100 are presented as 100% and no percentages are presented for zero frequencies. Where individual variable values are missing, summaries of categorical data are based on reduced denominators (i.e., the denominators include only patients with available data) and the number of missing values is presented. For summaries of AEs and concomitant medications (CM), the percentages are based on the total number of patients in each treatment group.

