#### **6.3.4. Safety Population**

Safety analyses are based on all enrolled patients. The safety population includes all patients who received at least 1 dose of randomized study drug in Year 1. The safety population is used for evaluation of safety variables. Patients who received at least one dose of bardoxolone methyl will be classified in the bardoxolone methyl group. Patients who received at least one dose of placebo and no dose of bardoxolone methyl will be classified in the placebo group. The safety population is based on this definition for both the Year 1 and Year 2 analyses.

Safety population treatment groups will not be modified after the Year 1 analysis. Patients in the placebo group receiving a dose of bardoxolone methyl in Year 2 are listed.

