## 7. STUDY POPULATION

### 7.1. Subjects Disposition

A disposition summary includes the number and percentage of patients in all analysis populations in the following categories:

#### Disposition - Year 1

- Per-protocol Population – Year 1
- Completed treatment through Week 48
- Discontinued treatment prior to Week 48
  - reason for discontinuing treatment
- Completed study follow-up through Week 52
  - on-treatment
  - discontinued treatment early but completed in-person study visits
  - continued to Year 2 follow-up
- Terminated from the trial before Week 52
- Follow-up by Year 1 study week
  - discontinued treatment
  - follow-up in-clinic
  - follow-up phone

#### Disposition - Year 2

- Per-protocol Population – Year 2
- Received at least one dose in Year 2
- Completed treatment through Week 100
- Discontinued treatment prior to Week 100
  - reason for discontinuing treatment
- Completed study follow-up through Week 104
  - on-treatment
  - discontinued treatment early but completed study visits
- Terminated from the trial before Week 104
- Follow-up by Year 2 study week

- discontinued treatment
- follow-up in-clinic
- follow-up phone

Patients who completed follow-up are defined as those who were followed by phone or in-person through the Week 104 visit. A listing of disposition is provided for all enrolled patients.

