### 10.1. Adverse Event Preferred Term and Body/Organ System Summary Tables

AEs are summarized by treatment as defined by the safety analysis set. In addition to being summarized by treatment year, AEs are also summarized overall. General considerations for AE summaries and calculations are:

- Multiple events by preferred term (PT) and system organ class (SOC) are counted once only per patient for summaries of AE incidence.
- For summaries of AE incidence by severity, only the most severe event is counted per patient.
- For summaries of AE incidence by relationship, only the most related event is counted per patient.
- An AE with a missing resolution date or incomplete date that is not identified as continuing is assumed to be continuing and no duration is calculated.
- Treatment-emergent adverse events (TEAEs) are summarized separately from off-treatment adverse events (OTAEs).
- For summaries of the number of AE events, all AEs are counted.

AEs are coded using MedDRA (Medical Dictionary for Regulatory Activities) version 19.1. In MedDRA, each verbatim term is mapped to a preferred term and high level term (HLT), which is then mapped to a system organ class. Tables and listings will present data at the SOC and PT level.

Treatment-emergent adverse events (TEAEs) are events that either:

- Have a date of onset on or after the date of the date of first dose and not more than 30 days after the date of the last dose of study drug, or
- Have no recorded date of onset with a stop date after the first dose of study drug, or
- Have no recorded date of onset or stop date

AEs with an onset greater than 30 days after the last dose of study drug, and therefore not treatment-emergent AEs (TEAEs), are classified as off-treatment AEs (OTAEs). Analyses described for TEAEs are also performed for OTAEs and tabulated separately.

The investigator grades the severity of the AEs as mild, moderate, or severe as defined in the study protocol. The investigators graded association or relatedness to the study medication according to criteria specified in Section 11.4 of the study protocol.

As defined in the protocol, a serious adverse event (SAE) is an adverse event that results in any of the following:

- Death;
- A life-threatening adverse drug experience;
- Inpatient hospitalization or prolongation of existing hospitalization;
- Results in persistent or significant incapacity or substantial disruption of the ability to conduct normal life functions;

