#### **10.1.2. Summaries of Adverse Events**

TEAEs and OTAEs are summarized by treatment based on year of AE onset, and overall. For each treatment, SOC, and PT, the number and percentage of patients reporting an event is calculated. In summary tables, SOC is presented alphabetically and events within SOC are presented by decreasing frequency count.

Summary tables (number and percentage of patients and events) of AEs (by SOC and PT) are provided by treatment as follows:

- All treatment-emergent AEs
- All treatment-emergent related AEs (definitely, probably, or possibly related)
- All treatment-emergent AEs by severity
- All treatment-emergent serious adverse events (including deaths)
- All related treatment-emergent serious adverse events (including deaths)
- All treatment-emergent adverse events leading to permanent discontinuation of study drug

Listings are provided showing:

- All AEs
- Serious adverse events (including deaths)

- AEs leading to permanent discontinuation of study drug

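### Year 2 and off-treatment adverse event percentages divide by all dosed patients, including those with little or no time at risk, so unequal early stopping would distort the comparison between arms

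*SAP*

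**What the plan says.** SAP section 6.2 sets the denominator: "For summaries of AEs and concomitant medications (CM), the percentages are based on the total number of patients in each treatment group". Section 10.1 says which groups are meant: "AEs are summarized by treatment as defined by the safety analysis set". Section 6.3.4 defines that set, "The safety population includes all patients who received at least 1 dose of randomized study drug in Year 1", and carries it forward: "The safety population is based on this definition for both the Year 1 and Year 2 analyses".

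Section 10.1.2 splits the tables by period, "TEAEs and OTAEs are summarized by treatment based on year of AE onset, and overall", and names the statistic: "For each treatment, SOC, and PT, the number and percentage of patients reporting an event is calculated". Under section 10.1 an event is treatment-emergent up to 30 days after the last dose. Off-treatment events are "AEs with an onset greater than 30 days after the last dose of study drug".

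Neither document gives a denominator specific to Year 2 or to the off-treatment period, a rate per patient-time, or a time-to-event summary of adverse events. Section 7.1 does count patients who "Received at least one dose in Year 2", but only as a disposition line.

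**The concern.** A percentage is easiest to read when everyone in the denominator could have had the event. That fails here in two opposite ways.

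In the Year 2 TEAE tables, a patient who stopped for good in Year 1 can contribute an event only if the 30-day tail runs into Year 2, yet counts fully in the denominator. The SAP expects such patients: section 3.1 of its addendum changes the exposure covariate because they have no Year 2 last-dose date.

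In the OTAE tables, the patients at risk are mostly the early stoppers, who under section 6.5.4.1 are asked to keep attending visits. Completers have almost no scheduled follow-up beyond day 30 but stay in the denominator.

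Section 3.1.2.1 lists safety through Week 104 as a Year 2 primary endpoint, and section 10 plans no formal safety testing. The printed numbers and percentages are thus the main basis for comparing the arms. If stopping differs by arm, part of a printed difference would reflect who was still at risk. The SAP is more careful elsewhere: section 6.5.4.1 confines off-treatment laboratory, vital sign and ECG summaries to patients who stopped before Week 100, timed from their last dose.

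**Working it through.** The documents state no adverse event percentage and no stopping rate, so there is no figure of the plan's own to reproduce. The visit days and arm sizes come from the SAP; the stopping shares and event risks are assumptions.

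**Completers' off-treatment follow-up** (SAP Table 2). Week 100 is Day 700±3, i.e. 697 to 703. Week 104 is Day 728 with up to 6 days earlier allowed, i.e. 722 to 728.
- Shortest gap: 722 − 703 = 19 days.
- Target: 728 − 700 = 28 days.
- Longest gap: 728 − 697 = 31 days.

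OTAEs need onset after day 30, so by the schedule a completer has at most about one day at risk.

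**Printed percentages.** Let d be the share of an arm that stopped in Year 1, and r the TEAE risk among those still at risk in Year 2. Let s be the share followed more than 30 days after last dose, and q the OTAE risk among them. Neglecting the tail:
- printed Year 2 TEAE % = r × (1 − d)
- printed OTAE % = q × s

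With equal true risks, r and q cancel. The Year 2 ratio is (1 − d_drug)/(1 − d_placebo) and the OTAE ratio is s_drug/s_placebo. The table sets s = d, meaning that all Year 1 stoppers stay in follow-up and Year 2 stoppers are ignored.

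| Assumed early stopping, drug vs placebo | Year 2 TEAE ratio | OTAE ratio |
|---|---|---|
| 5% vs 5% | 0.95/0.95 = 1.00 | 0.05/0.05 = 1.0 |
| 10% vs 5% | 0.90/0.95 = 0.95 | 0.10/0.05 = 2.0 |
| 20% vs 8% | 0.80/0.92 = 0.87 | 0.20/0.08 = 2.5 |
| 20% vs 5% | 0.80/0.95 = 0.84 | 0.20/0.05 = 4.0 |
| 30% vs 10% | 0.70/0.90 = 0.78 | 0.30/0.10 = 3.0 |

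The arm labels are arbitrary, because the documents do not say which arm would lose more patients.

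**Example at 20% vs 8%, true risk 50% in both arms.**
- Year 2 TEAEs print as 0.80 × 50% = 40% vs 0.92 × 50% = 46%.
- OTAEs print as 0.20 × 50% = 10% vs 0.08 × 50% = 4%.
- With at-risk denominators, both tables show 50% vs 50%.

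If the true Year 2 risks were 55% vs 50%, the table would print 0.80 × 55% = 44% vs 46%.

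**Precision.** With 78 and 79 patients (section 4.3.1), the 95% margin for a difference near 50% is 1.96 × √(0.25/78 + 0.25/79) ≈ 0.156, about ±16 points.

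**The 30-day tail.** A patient who takes the last dose at Week 48 (Day 336±3, i.e. 333 to 339) and never restarts has treatment-emergent status to Day 363 to 369. Week 52 is Day 364 at the latest, so the tail can cross it.

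**The case against.** The strongest defence is that the fixed denominator is a legitimate choice. It gives the share of all treated patients with a reported event in the period, and it keeps the groups close to those randomized. Taking Year 2 drug is a selection after randomization. If stopping is related to toxicity, restricting to continuers removes the susceptible patients and can itself flatter the more toxic arm. This stands: it is a reason to keep the planned percentages and add to them.

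Much of what a reader needs is also planned: overall tables, counts of patients and events, listings of all events, exposure duration, and disposition including Year 2 dosing. Year 2 percentages can be roughly rescaled from these. Off-treatment patient-time cannot readily be recovered, so the defence is weakest for OTAEs.

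Three stronger readings are tempting, and the documents do not support them.
- A reader might infer that the arm with more early stoppers will look safer in Year 2 and worse off treatment. No stopping rates are given, and the printed direction also depends on the true risks.
- A reader might take the 44% vs 46% example as a reversed safety conclusion. A move from +5 to −2 points lies well inside ±16 points. The OTAE example is about 8 vs 3 patients.
- A reader might infer that every randomized patient is in the denominator, or that a Year 1 stopper's later events are lost. The denominator is dosed patients, and events beyond 30 days go to the OTAE tables and the listings.

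The 19-day gap pairs the latest last dose with the earliest visit; the plan aims for 4 weeks. The SAP addendum also removes the upper limit of the Week 104 eGFR window, so some completers may be seen after day 30. The protocol text available is only the COVID-19 addendum, so rules for reporting events after the last visit cannot be checked. That completers have almost no OTAE time at risk is therefore a statement about the visit schedule.

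**Conclusion.** The point holds in a conditional form. As written, the Year 2 TEAE and OTAE percentages are diluted by patients with little or no time at risk. The distortion between arms depends on unequal early stopping. With equal stopping the ratios are undistorted, although the percentages still sit below the risk among patients at risk.

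Over the assumed range of 10% vs 5% to 20% vs 8%, and with equal true risk, the Year 2 TEAE ratio is 0.95 to 0.87, a modest effect. The OTAE ratio is 2.0 to 2.5, because that percentage mainly reflects the share of early stoppers. The OTAE figures also assume that early stoppers stay in follow-up and that completers follow the visit schedule.

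No formal test or efficacy conclusion is affected. This is a low-cost improvement to the reporting of a stated Year 2 primary safety endpoint, and it matters most for the OTAE tables.

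**What to change.** Amend SAP sections 6.2 and 10.1.2 as follows.

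1. Keep the all-treated percentages for Year 1 and overall TEAEs. They may also stay for Year 2 TEAEs.
2. State the boundary between Year 1 and Year 2 for event onset; the text supplied does not define it.
3. For Year 2 TEAEs, show the number at risk: patients with at least one Year 2 dose, or still within 30 days of last dose at the start of Year 2. The second clause matters because, without it, a tail event could be in the numerator while the patient is outside the denominator.
4. For OTAEs, use as denominator the patients followed more than 30 days after last dose.
5. Add patients with event per 100 patient-years at risk to the Year 1, Year 2, OTAE and overall tables. This also handles patients with only brief follow-up, such as a completer seen on day 31, whom item 4 alone would count in full.
6. Footnote that the at-risk subsets are selected after randomization and must be read with the disposition table.

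The cost is SAP wording, table shells and programming. The dosing, onset and follow-up dates needed are already part of the trial data, and no planned table is lost.

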### **6.3. Analysis Populations**

Analysis populations defined in this section pertain to patients enrolled in the Phase 3 portion of the trial.

#### **6.3.1. ITT Population**

The intent-to-treat analysis set is defined as all enrolled patients categorized by their randomized treatment group (whether or not they received study drug). Note that this is the same definition for both the Year 1 and Year 2 analyses.

#### **6.3.2. Per-Protocol (PP) Population – Year 1**

A sensitivity analysis exploring the robustness of the primary ITT findings of Year 1 endpoints is based on the patients in the per-protocol, Year 1 population.

The per-protocol (Year 1) population is defined as patients who:

- Received study drug through Week 48; and
- Had no protocol deviation that could potentially affect the efficacy conclusions.

Review of protocol deviations for determining the Year 1 per-protocol population will be performed by a blinded team prior to Year 1 database lock.

#### **6.3.3. Per-Protocol (PP) Population – Year 2**

A sensitivity analysis exploring the robustness of the primary ITT findings of Year 2 endpoints is based on the patients in the per-protocol, Year 2 population.

The per-protocol (Year 2) population is defined as patients who:

- Received study drug through Week 100; and
- Had no protocol deviation that could potentially affect the efficacy conclusions.

Review of protocol deviations for determining the Year 2 per-protocol population will be performed by a blinded team prior to the final database lock.

#### **6.3.4. Safety Population**

Safety analyses are based on all enrolled patients. The safety population includes all patients who received at least 1 dose of randomized study drug in Year 1. The safety population is used for evaluation of safety variables. Patients who received at least one dose of bardoxolone methyl will be classified in the bardoxolone methyl group. Patients who received at least one dose of placebo and no dose of bardoxolone methyl will be classified in the placebo group. The safety population is based on this definition for both the Year 1 and Year 2 analyses.

Safety population treatment groups will not be modified after the Year 1 analysis. Patients in the placebo group receiving a dose of bardoxolone methyl in Year 2 are listed.

#### **6.3.5. Japanese Population**

The Japanese population includes all patients enrolled at sites located in Japan. A sensitivity analysis exploring safety and efficacy in Japanese patients is performed as appropriate using the

Japanese population. The Japanese population is used for evaluation of efficacy and safety overall and by relevant subgroups to support potential future regulatory submissions to PMDA in Japan.

## **6.4. Baseline Definition**

Baseline values are defined as the last non-missing assessment prior to the first study drug administration, unless otherwise specified below. If the first study drug administration occurs after the date of randomization, the last measurement prior to the first study drug administration is considered the Day 1 measurement for the calculation of baseline. Assessments without time-stamp collected on the same date as the first date of study drug administration are considered to occur before the first dose of study drug administration.

### **6.4.1. Estimated Glomerular Filtration Rate**

Baseline eGFR is defined as the average of screening and Day 1 eGFR measurement, calculated as shown below:

- Screening eGFR = average of the last two eGFR measurements collected prior to the Day 1 eGFR collection
- Day 1 eGFR = the measurement on the date of first study drug administration prior to the first study drug administration
- Baseline eGFR =  $(0.5 \times \text{Day 1 eGFR}) + (0.5 \times \text{Screening eGFR})$

